Occupational Therapy's Role in Promoting Community Wellness Utilizing Sit-Stand Workstations

NCT03052426

IRB Approval Date: 2/2/2017

West Virginia University - Office of Research Integrity and Compliance Protocol Number: 1612397536 Principal Investigator: [name]

Protocol Questionnaire

Human Subject Research

Does the protocol meet the federal definition of research? For help determining the type of research you are conducting, see the DHHR Human Subject Regulations Decision Charts at http://www.hhs.gov/ohrp/policy/checklists/decisioncharts.html. Yes

Does the research involve living person(s)?

Yes

Will information from individual person(s) be collected as part of this research?

Yes

Funding Source

Is there a secured funding source?

No

Locations of Research

Will the research take place at an off campus location?

No

Select the location(s) where the research will be conducted. At least one location must be selected.

WVU Campus

Will this study require an Inter-Institutional Authorization Agreement (IAA)?

No

Design

Does the research involve surveys/interviews/questionnaires? If so, attach a copy of the interview/survey questions on the Notes & Attachments page. Yes

Will you be asking any questions that are likely to distress your subjects (e.g., questions about abuse, trauma, or suicide ideation)? If so, attach counseling services referral list on the Notes & Attachments page.

Please provide a lay summary (written at 6th grade level) that includes a statement about the purpose and the general aims of the research.

The aim of this study is to combat the growing global health issue of sedentary behavior and the associated health consequences of prolonged sitting in the workplace. The population of desk-based workers makes up a relatively large population and are an important target for this health promoting initiative with a focus on improving posture, encouraging movement, and fostering a more active and healthy business community. It's important to recognize that occupational therapy practitioners can contribute to community health promotion/disease prevention programs by the skill-set of practitioners to understand habits and routines that influence the adoption and maintenance of healthy behaviors.

Fully describe all procedures to be performed, from start to finish, numbering your procedures 1,2,3 or A, B, C (e.g., 1. Recruiting, 2. Consent, 3. Collecting data, 4. How findings will be shared, etc.).

1. Obtain IRB approval 2. Distribute fliers around the HSC building and send an email through the wellness office to all faculty and staff in the HSC building. 3. Make an Excel file of all interested participants. 4. Contact participants to ensure eligibility. 5. Randomly assign participants to one

of three groups: (1) Sit-Stand station with 4-6 educational sessions and instructions to alternate standing and sitting every 90 minutes, (2) Sit-stand station with 4-6 educational sessions and instructions to stand for 20-30 minutes every hour, (3) Sit-stand station with 4-6 educational sessions with instructions to alternate sitting and standing every hour. *all groups will attend same educational sessions. 5. Schedule meeting to review and collect informed consent documents and distribute and collect the Stages of Change Questionnaire, the Cornell Musculoskeletal Discomfort Questionnaire, and the Movement at Work Questionnaire. 6.Install sit-stand work stations in each participants office space. 7. Provide educational sessions on use of sit-stand workstations and the behavioral monitoring self-report form. 8. Within 2 weeks of installation of sit-stand workstation complete observation with each participant to ensure safe and efficient use. 9. Collect behavioral

monitoring self-report forms weekly from all participants. 10. Send reminder email or text prompts to participants for designated time intervals for the group which they are enrolled. 11. After 3 months re-distribute the Stages of Change Questionnaire, Cornell, and Movement at Work Questionnaires. 12. After 6 months re-distribute the Stages of Change Questionnaire, Cornell, and Movement at Work Questionnaire, and Movement at Work Questionnaire, Cornell, and Movement at Work Questionnaire, Cornell, and Movement at Work Questionnaires and collect all sit-stand workstations. 13. Clean and analyze data. 14. Write up report and prepare for presentation or publication.

Please describe the investigational procedures that will be performed throughout the duration of the study.

Observation of participants in natural working environment, questionnaires/surveys.

Please describe the standard of care procedures that will be performed throughout the duration of the study.

All participants will be given the same questionnaires/surveys and behavioral tracking forms. All participants will also receive the same education on the use of the sit-stand workstation and other helpful office ergonomic tips.

Will you be assigning or randomizing participants to groups or conditions (e.g., control, placebo)?

Yes

Describe the group assignment.

All the groups will receive the same educational sessions and complete the same questionnaires. The only difference in groups is in the instructions for alternating sitstand time. One group will alternate every 20-30minutes, one every 60 minutes, and one every 90 minutes.

Describe what is known about this topic and why this study is needed. Please include at least two reference citations to support your rationale.

Prolonged sedentary activity and a reduction in human energy expenditure are detrimental to many domains of health. In recent years, "populations have become increasingly sedentary, with many adults spending a minimum of 70% of their waking hours sitting" with little neuromuscular stimulation (Owen, Sparling, Healy, Dunstan and Matthews, 2010). Desk-based workers make up a relatively large proportion of this population making them an important target for health promotion initiatives focusing on solutions to implement healthy workspaces and foster a more active business community. Although there is rich literature on the many benefits of reducing sedentary behavior, there is a call for further research on the feasibility and long-term effects of sitstand desks on achieving this reduction in office settings (Grunseit, et al., 2012). Occupational therapy practitioners have the capacity to address this health issue with their background in community disease prevention and health promotion to improve an individual's wellness and quality of life. More research is also needed to establish the specific role of occupational therapy in workplace wellness interventions and apply

occupation in its natural settings such as the workplace by maximizing performance, function, and wellness. By implementing sit-stand work stations with educational sessions into offices of desk-based employees long-term, we will better be able to analyze how effective this strategy is at decreasing sitting time and measure health and behavioral outcomes associated with using this intervention. Grunseit, A. C., Chau, J. Y.-Y., van der Ploeg,

H. P., & Bauman, A. (2013). "Thinking on your feet": A qualitative evaluation of sit-stand desks in an Australian workplace. BMC Public Health, 13, 365. Owen, N., Sparling, P. B., Healy, G. N.,

Dunstan, D. W., & Matthews, C. E. (2010). Sedentary Behavior: Emerging Evidence for a New Health Risk. Mayo Clinic Proceedings, 85(12), 1138-1141. doi:10.4065/mcp.2010.0444

What method are you going to use to analyze the data?

Data will be coded and analyzed using a statistical software program. Any qualitative data that is collected will be member checked.

Expedited Review

Is this study only minimal risk?

Yes

Does the research qualify for Expedited Review Category 1 - use of FDA-approved medical device?

Does the research qualify for Expedited Review Category 2 - blood sample collection?

No

Does the research qualify for Expedited Review Category 3 - noninvasive collection of biological specimens?

Does the research qualify for Expedited Review Category 4 - noninvasive standard care procedures?

No

Does the research qualify for Expedited Review Category 5 - evaluation of data (e.g., medical records review)?" No Does the research qualify for Expedited Review Category 6 - voice, video, digital, or image recordings?

Does the research qualify for Expedited Review Category 7 - behavior, surveys, interviews, etc.?

Briefly describe how the research meets the requirements of the expedited category(ies) selected.

Participants will be required to complete multiple questionnaires as they participate in the intervention. The questionnaires will be assessing changes in behavior, movement at work, and discomfort at work.

Will subjects intentionally be deceived as to the purpose of the study?

No

Does the study involve intervention and/or manipulation of the subjects or the subjects' environment (e.g., educational intervention or training, experimental or quasi-experimental design)? Yes

Describe how and where researchers will interact with participants, explaining how these interactions will be kept private.

Researchers will interact with participants on an individual basis in the participants private office space. In the event that the participant does not have a private office a private space will be reserved at the participants request.

Describe and assess any potential possibilities for risk or harm to the subjects as a result of their participation in the research, including discomforts, hazards, or inconveniences to the subjects. The primary inconvenience for the participants will be the need for them to clear a space to install the sit-stand work station at their desks. Depending on what group the participant is in, they will be asked to track how often they stand throughout the day which could be an inconvenience or potential discomfort. The sit-stand desk does have mechanical parts that could potentially pinch or injure a participant if not used correctly.

Is the research categorized as interventional medical research? No

HIPAA

Does the research involve protected health information (PHI)?

Yes

Will the HIPAA and consent forms be combined? If not, attach a separate HIPAA Authorization to the Notes & Attachments page. Yes

Are you requesting a HIPAA waiver? If yes, attach a HIPAA Waiver Form on the Notes & Attachments page.

No

Will the research being conducted at a covered entity require authorization from the subject? If yes, attach a HIPAA Form on the Notes & Attachments page - only if a combined consent with HIPAA is not used.

Are you transferring identifiable data to or from another institution? If yes, attach a signed and WVU Legal Counsel approved HIPAA Data Use Agreement Form on the Notes & Attachments page.

Will the research being conducted at a covered entity involve data that is de-identified? If yes, attach a HIPAA De-Identification Certification Form on the Notes & Attachments page. You can find the form here (this is only for NHSR studies). No

Will the study include deceased individuals? If yes, attach a HIPAA Decedents Form on the Notes & Attachments page.

Will data/samples with identifiers be received from another entity? If yes, attach a signed, Legal Counsel approved HIPAA Data Use Agreement Form on the Notes & Attachments page.

No

Subjects

Will any of the subjects be less than 18 years old?

No

Indicate the maximum number of subjects to be enrolled or medical records to be reviewed at all sites by the WVU or VAMC research team. 20

Provide a rationale for choosing your sample size.

This study will consist of 3 groups of 6 individuals receiving the sit-stand workstation. The workstations are being donated to us to complete the research. And 18-20 workstations is the max that we can receive.

State the requirement(s) to become a participant in the study (e.g., age range, sex, language spoken, class enrollment/ranking).

Participants must spend > 50% of their work day seated at the computer. Participants can be male or female and must be ages 18 years or older. Participants must be primarily English speaking. Participants must work within the Health Sciences Center building at West Virginia University.

Explain why selection of participants will be equitable addressing gender, ethnicity, and/or race of subjects.

Attempts will be made to choose 50% males and 50% females for the study. However, given

the nature of the work it is probable that we will have a higher percentage of females than males enrolled. No one will be ineligible based on race or ethnicity.

In outline format and chronological order, describe what will be done to identify and recruit participants (e.g., A, B, C or 1, 2, 3).

1. Fliers will be distributed throughout the HSC building and an email will be sent from the wellness program to all HSC faculty and staff. 2. Interested participants will contact a member of the research team who will verify their eligibility to participate. 3. If eligible, participants will placed on

a list in Excel with an email address or phone number to be contacted. 4. Participants will then be randomly drawn from the list and contacted to participate in the study. The team will draw 9-10 males and 9-10 females to participate. 5. In the event that there are 20 or fewer participants who are eligible all will be contacted to participate regardless of gender.

Will your study target any of the following vulnerable groups: cognitively impaired, pregnant women and fetuses, or prisoners?

No

Does this research involve participants who could be coerced or unduly influenced, such as current students/employees of research team members? No

Does the protocol deal with cancer prevention, treatment, or diagnosis (including surveys)?

No

Has this protocol been reviewed by Clinical Trials Working Group (CTWG)? If yes, please attach the CTWG's correspondence on the Notes & Attachments page. No

Consent Procedures

Will SIGNED informed consent be obtained from subjects (all or in part)?

Yes

Will the informed consent form be translated into any other language(s)?

No

Is a waiver of informed consent being requested (i.e., there will be no consent process at all)?

No

Describe the consent process (using 1, 2, 3 or A, B, C), addressing when, where, and how participants will be informed.

1. Once a participant is determined to be eligible he/she will be contacted by a member of the research team to set up a time to meet in a private space to go over the informed consent form. 2. Eligible participants will review the consent form and will be given the opportunity to ask any questions. 3. The member of the research team will answer any questions or clarify any areas on the form that need to be clarified. 4. Once there aren't any more questions and the participant is comfortable with the details of the study, the participant and research team member will sign the form. 5. Once the form has been signed the participant will place their master code (explained in the confidentiality section) on the consent form and remit it to one of the research team members.

Are you requesting an alteration of consent (e.g., short form, braille consent or witnessed verbal consent)?

Indicate who will be consenting subjects and describe the process of training all personnel who will be obtaining consent.

The PI or any of the Co-I's will be responsible for consenting subjects for the study. All of them have completed the required CITI trainings.

Is a waiver of the requirement to obtain written documentation of the consent process being requested (if yes, attach the information to be provided to the participants)? No

Potential Benefits

Is there any known benefit to the individual subject as a result of participating in the research? Payments to subjects should not be included in this section, but addressed in the Payments/Reimbursements section.

Subjects will get to trial a sit-stand workstation free of cost during the timeframe in which they participate in the study. Potential benefits that can occur from the use of the sit-stand work station include but are not limited to: decreased discomfort with work tasks, increased productivity, decreased muscle strain, improved circulation, and increased energy.

Describe the potential benefit(s) to society and/or scientific / medical knowledge of the planned work.

Most studies that have examined the use of sit-stand work stations have not looked at the dose of sitting versus standing to determine if there is a difference. By examining this relationship we may be better able to provide guidelines for the use of this type of equipment.

Confidentiality

Does this study have a Federal Certificate of Confidentiality? If yes, attach the certificate on the Notes & Attachments page.

At any point during this study, will identifiable data be viewed or recorded?

Yes

Data must be kept for a minimum of three (3) years after study completion. In addition to the required 3 years, how much longer will the data be kept? Data will only be kept for the minimum of 3 years.

Where will data be securely located?

The data will be securely located in a locked filing cabinet in the PI's office.

How will data be destroyed?

Data will be shredded upon reaching the 3 year timeframe.

Will anyone other than the PI, research team members, or IRB have access to the identifiable data (e.g., sponsor/funding source, other collaborators)? No

Describe the steps that will be taken to maintain the privacy of subjects (e.g., where interaction takes place) and the confidentiality of data (e.g., master code). Subjects will be provided with directions to create a master code from a member of the research team that will be used when they complete and return any questionnaires or

forms, including the consent form, related to the study. The master code will consist of the first two letters of the first name, last two digits of birth year, and first two letters of last name. The consent forms containing the master codes will be kept and stored separately from the data.

Financial Considerations

Will the subject be paid (money, gift certificates, coupons, etc.) to participate in this research project?

No

Will the subjects incur any costs to participate in this project (e.g., travel, physician fees, study procedures, study drugs)? No

Will WVU students receive extra credit for participating in this research project?

No

Advertisements

Will there be advertisements for this study?

Yes

Select all the types of advertisement methods that will be utilized. For assistance with creating protocol advertisements, utilize the Advertisement Checklist on the ORIC website http://oric.research.wvu.edu/r/download/6466. Flyer, Recruitment Letter

Describe where the ad(s) will be placed and attach a copy of the advertisement(s) on the Notes & Attachments page.

The flyer will be posted around the Health Sciences Center building. The recruitment letter will be sent through the employee wellness office to staff and faculty at the HSC building.

Sample Collection

Will sample(s) be used?

No

Biological Safety

Does the study involve the handling of any infectious and/or non-infectious agents or recombinant DNA?

Data Protection for IRB

Does the project have data protection requirements?

No

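### As listed, random assignment comes before consent and the first questionnaires, and no section supplied places it later or says the arm is hidden until then

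*Combined protocol and SAP*

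**What the plan says.** The form asks for a numbered account of the procedures covering the study from beginning to end. In the answer, the eligibility contact is followed at once by assignment: "4. Contact participants to ensure eligibility. 5. Randomly assign participants to one" of the three groups. A second entry with the same number then reads "5. Schedule meeting to review and collect informed consent documents and distribute and collect the Stages of Change Questionnaire", followed by the Cornell and Movement at Work questionnaires. Installation is step 6. The next step written as arm-specific is step 10: "Send reminder email or text prompts to participants for designated time intervals for the group which they are enrolled".

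The recruitment outline in the Subjects section says "Participants will then be randomly drawn from the list and contacted to participate in the study". It adds: "In the event that there are 20 or fewer participants who are eligible all will be contacted to participate regardless of gender". The Consent Procedures section begins "Once a participant is determined to be eligible he/she will be contacted by a member of the research team to set up a time" for the consent meeting, and says that the PI or any Co-I "will be responsible for consenting subjects for the study". On the use of the questionnaires, the Expedited Review section says only this: "The questionnaires will be assessing changes in behavior, movement at work, and discomfort at work".

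**The concern.** Consent and first measurements normally come before randomisation, so that neither can be affected by the arm. Here the listed order is the reverse, which has two possible consequences.

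- **Refusals.** Anyone who declines at the consent meeting has already been assigned and is lost after randomisation. If the arm is known, willingness to take part could differ between arms, and the groups that start the study would no longer be those that chance created.
- **First answers.** All three questionnaires are self-reported. If participants know their interval instruction when they first complete them, their answers could shift with it. If those answers serve as the baseline, the shift enters that arm's measured change.

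The groups are planned at 6 people each, so a few refusals or shifted answers would carry weight.

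**Working it through.** The plan gives no figure to reproduce. The check sets the sections side by side.

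**1. Order in the procedures list.** Excel file of interested people (3); eligibility contact (4); random assignment (first 5); consent and first questionnaires (second 5); installation (6); education (7); observation (8); weekly forms (9); prompts (10). Assignment precedes consent.

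**2. Does any other section reverse this?**
- The group-assignment answer describes how the arms differ. It is silent on when assignment happens and when it is disclosed.
- The draw in the recruitment outline selects people from the list. It does not allocate them to arms.
- The consent section goes from eligibility to the consent meeting without mentioning assignment.
- No section mentions concealment or blinding.

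So nothing reverses the order, and nothing hides the arm from the participant or from the person taking consent.

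**3. How reliable is the list as a chronology?** Only partly.
- The number 5 is used twice.
- The procedures list makes the Excel file first and checks eligibility second; the recruitment outline verifies eligibility first and lists people second.
- The procedures list omits the random draw that the recruitment outline contains.
- Steps 9 and 10 are continuing activities, not events that follow step 8.

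**4. Scale of one refusal.** The sample-size rationale gives 3 groups of 6, that is 3 × 6 = 18. One person lost after assignment is 1/6 = 16.7% of an arm. The documents give no refusal rate and no replacement rule, so the number of refusals is unknown.

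**5. Effect of a shift in first answers.** For one arm, mean change = mean later score − mean first score. If knowledge of the arm moves that arm's mean first score by d, its mean change moves by −d, and its contrast with an unaffected arm moves by the same amount. With 6 people, a shift of x in one person gives d = x/6. The documents give no value for x. They also do not say that the analysis uses change from first answers; the data-analysis answer names no method.

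**6. Arm sizes from one even draw after all meetings.** 20 people: 7/7/6. 19: 7/6/6. 18: 6/6/6. 17: 6/6/5. 16: 6/5/5. 15: 5/5/5.

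**The case against.** The strongest reply is that the list is too loosely drafted to prove the intended order. It conflicts with the recruitment outline over the two entries just before assignment, it repeats a number, and the consent section goes straight from eligibility to consent. That stands as a limit on certainty. It does not remove the point, because the order that is written puts assignment first and nothing corrects it.

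A second reply is that the harm is conditional. All arms receive the same workstation, education and questionnaires and differ only in the interval instruction, which may limit arm-related refusal. This also stands in part. Against it, the risk description says that tracking of standing depends on the group and may be inconvenient or uncomfortable. That fits poorly with the procedures list, where every participant returns the forms, but it means that equal burden across arms cannot be taken as settled.

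A reader might infer three stronger things that the documents do not support.

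- **That participants or staff know the arm at the consent meeting.** No section says so, or says when participants are told.
- **That the consent form is silent on this.** It was not in the supplied text, so nothing can be held against it.
- **That reordering by itself gives more even arms.** Evenness depends on how assignment is made, not on when. If 18 people are assigned 6/6/6 and two, unrelated to arm, then refuse, an arm falls to 4 with probability 3 × C(6,2)/C(18,2) = 45/153 = 29%. Simple randomisation of the remaining 16 after consent gives 6/5/5 with probability 3 × 2,018,016/3^16 = 14%, and so an arm of 4 or fewer with probability 86%. Better balance is not a reason for the change; protection from arm-dependent refusal and first answers is.

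**Conclusion.** The point holds in this form: the listed order is assignment, then consent and first questionnaires, and no section supplied reverses it or conceals the arm. Confidence is high for that.

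Confidence is medium for the consequence. Loss of decliners after randomisation follows directly if the list is followed. Arm-dependent refusal or first answers requires in addition that the arm is known at the meeting, and any effect on results requires that the first answers serve as the baseline. Neither condition can be settled from the documents, and the size of any bias cannot be computed.

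The change is worth making because it costs little. Even if assignment was always meant to follow consent, the text needs correcting, since it says otherwise.

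**What to change.** Reorder and renumber the procedures list: eligibility and draw, consent, completed first questionnaires, random assignment, installation. Align it with the recruitment outline on when the Excel list is made. Add one sentence to the consent section saying that no arm exists, or is known to anyone at the meeting, until the signed consent and the three questionnaires have been returned.

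**Preferred method.** Finish all consent and questionnaire meetings. Replace decliners from undrawn people on the recruitment list, where there are any; if 20 or fewer are eligible, all are contacted and there is no reserve. Then make one even random draw to the three arms, with sizes differing by at most one. With no sequence to guess, this needs no envelopes.

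**If enrolment must be staggered.** Use a concealed list prepared by a team member who does not take consent, with block sizes varied and not disclosed to those who do. Fixed blocks of 6 with two places per arm would not serve. In an open study, staff who know the earlier assignments could deduce the last place in each block, which is 3 of 18 places, and in 3/15 = 20% of blocks the fifth as well.

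**Cost.** Protocol wording and one draw or list; no extra visits or participants. Under the preferred method, assignment and so installation wait for the last consent meeting, and the first answers of early participants are older by then. Under the staggered method, someone must hold the list. Neither method brings back people who refuse; it only ensures that they refuse before randomisation.

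### The rationale promises evidence on how well workstations plus education reduce sitting, but every arm gets both: that effect is only an uncontrolled before-after change, and randomisation compares schedules alone (minor)

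*Combined protocol and SAP*

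**What the plan says.** The answer on what is known and why the study is needed says of workstations with educational sessions that "we will better be able to analyze how effective this strategy is at decreasing sitting time". It is a rationale, not a formal objective. The document states no hypothesis, primary outcome or test, and the data-analysis answer says only that statistical software will be used.

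The first of the two procedure steps numbered 5 gives each of the three groups a workstation and 4-6 sessions. The group-assignment answer adds: "The only difference in groups is in the instructions for alternating sitstand time". The sample-size rationale has 3 groups of 6, all with a workstation, limited by a donated supply of 18-20.

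The second step 5, before installation at step 6, is to "distribute and collect the Stages of Change Questionnaire, the Cornell Musculoskeletal Discomfort Questionnaire, and the Movement at Work Questionnaire". These are repeated at 3 and 6 months (steps 11 and 12). Other data begin after installation:
- the weekly form: "7. Provide educational sessions on use of sit-stand workstations and the behavioral monitoring self-report form";
- the observation: "8. Within 2 weeks of installation of sit-stand workstation complete observation with each participant to ensure safe and efficient use".

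Prompts follow the group: "10. Send reminder email or text prompts to participants for designated time intervals for the group which they are enrolled".

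The societal-benefit answer states a different question, whether the dose of sitting versus standing makes a difference.

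One schedule is described in two ways. The procedures give group 2 "instructions to stand for 20-30 minutes every hour"; the group-assignment answer says "One group will alternate every 20-30minutes, one every 60 minutes, and one every 90 minutes".

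**The concern.** A controlled estimate of what the workstation and education do needs people who did not receive them over the same period. There are none. A pooled before-after change mixes any effect of the strategy with self-monitoring, expectation and time trend, and these data cannot separate them. If all three arms improved alike, a report written to the rationale sentence could credit the workstation and education with a change that has other causes. No section limits the conclusion to the schedule comparison.

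The schedule comparison is what randomisation supports, so the schedules need a single definition. At present one of the three has two.

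**Working it through.** **Figure in the plan.** There is no power calculation to reproduce. The stated arithmetic is 3 × 6 = 18, which fits the supply of 18-20 workstations and the enrolment maximum of 20.

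**What is observed.** Assuming full follow-up:
- before installation: 18 to 20 participants × 1 = 18 to 20 questionnaire assessments;
- after installation: 18 × 2 = 36 to 20 × 2 = 40 assessments;
- assessments at 3 or 6 months from anyone without a workstation: 0.

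A larger sample would not change the last line.

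**Before-after test with no strategy effect.** Assumptions: a shift of d SDs of the change score shared by all arms, and a two-sided 5% one-sample t-test on pooled change. Power is the noncentral t probability with n − 1 df and noncentrality d√n.

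| Assumed shift d | n=18: d√18 | P(significant) | n=20: d√20 | P(significant) |
|---|---|---|---|---|
| 0.25 | 1.06 | 0.17 | 1.12 | 0.19 |
| 0.50 | 2.12 | 0.52 | 2.24 | 0.56 |
| 0.75 | 3.18 | 0.85 | 3.35 | 0.89 |

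A shared shift moves all arm means equally and cancels from between-arm differences. If the schedules do not differ, the three-arm F-test therefore rejects with probability 0.05 at every d.

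**Precision of the schedule comparison.** Results are in SD units of the outcome analysed, assuming equal SDs and no dropout.
- Half-width, 6 versus 6, error pooled over three arms (15 df): t(0.975; 15) × √(2/6) = 2.131 × 0.577 = 1.23 SD.
- With 20 split 7/7/6 (17 df): 2.110 × √(2/7) = 1.13 SD, and 2.110 × √(1/7 + 1/6) = 1.17 SD.
- Detectable difference, 6 versus 6, two-sided 5%, 80% power (noncentrality δ√3, solved for δ): 1.73 SD with 15 df, or 1.80 SD with two arms alone (10 df).
- The same with Bonferroni for three pairs (α = 0.05/3): 2.07 SD (15 df) or 2.19 SD (10 df).

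**The two descriptions of one schedule.** Assume an 8-hour (480-minute) day and, for alternation, equal sitting and standing periods.
- Procedures wording: 8 × 20 = 160 to 8 × 30 = 240 minutes standing.
- Group-assignment wording: alternating every 20 or 30 minutes gives 240 minutes.

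The two agree at 30 minutes and diverge below it. On the same assumptions, alternating every 60 minutes gives 240 minutes. Alternating every 90 minutes gives 210 if the day starts seated or 270 if it starts standing. Under the group-assignment wording the three schedules therefore differ mainly in bout length. Under the procedures wording one of them may also differ in total standing time.

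**The case against.** The strongest reply is that the target is one soft background sentence. It promises only to be better placed to analyse effectiveness, and goes on to outcomes associated with use of the intervention. The same answer calls for work on feasibility, which before-after data can serve. The expedited-review answer says openly that the questionnaires assess changes. The societal-benefit answer already poses the dose question that the randomisation fits. All of this stands, and it is why the point is minor. It does not remove the gap between the sentence and the design.

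Three stronger readings are tempting and are not supported:
- A reader might infer that the protocol claims its randomisation tests the workstation. It nowhere says so.
- A reader might infer that arm-specific prompts bias the schedule comparison. If the randomised contrast is defined as the instruction plus its prompts, a response to prompts is part of what is compared.
- A reader might infer from the risk section, which makes tracking of standing depend on the group, that self-monitoring differs by arm. The procedures twice say otherwise: forms are collected weekly from everyone, and all participants receive the same tracking forms. The risk sentence may mean only that the burden varies with the schedule. It warrants a wording check, not a finding of bias.

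The shift sizes and the t-test are illustrative. The schedule conflict is a separate matter and does not cause the missing comparator.

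**Conclusion.** The concern holds as a wording point of minor severity. The design cannot give a controlled estimate of how far workstations plus education reduce sitting, because no arm goes without them. With an assumed shared shift of 0.5 SD of change and no strategy effect, a before-after test would be significant about half the time (0.52 to 0.56). Over assumed shifts of 0.25 to 0.75 SD the range is 0.17 to 0.89.

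The schedule comparison is protected from a shift common to all arms, but it is wide: half-width about 1.23 SD at 6 versus 6, with a detectable difference of 1.73-1.80 SD, or 2.07-2.19 SD with Bonferroni. These figures assume equal SDs and full follow-up. No SD or target difference is given, so they cannot be turned into minutes of sitting.

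The Movement at Work Questionnaire looks closest to sitting time, but its items are not in the text, so how directly it measures sitting is unknown. A reader might infer that the study is invalid or must add a control group. That does not follow: the dose question is stated, and the randomisation matches it.

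**What to change.** 1. Reword the rationale sentence, and write the report, so that the randomised inference is the comparison of the three schedules (instruction plus prompts), in line with the dose question. Give each difference with its confidence interval. Report pooled before-after change as uncontrolled and descriptive, not attributed to the workstation and education.
2. Before randomisation, reconcile the procedures and the group-assignment answer on the 20-30 minute schedule, so that one definition governs instructions, prompts and analysis. Which definition is for the investigators to settle.
3. Check the risk sentence on group-dependent tracking against the procedures and align the wording.

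These are text changes and need no extra participants, workstations or visits. The downside is a narrower claim: the study could no longer present itself as evidence on how well the workstation and education reduce sitting, and the comparison it keeps is imprecise.
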